The evaluation of our proposed trial, which integrates live coactive coaching with a software solution for cancer survivors, demonstrates a significant favorable balance between minimal risks and anticipated benefits. The residual risks are minimized through tailored safety measures and are outweighed by the expected benefits of improved physical health, decreased symptom burden, and enhanced quality of life.

Supporting this favorable assessment, a substantial body of research not only confirms the safety of exercise but also endorses the significance of physical activity and lifestyle

changes in cancer management. This evidence base, coupled with medical endorsement of physical activity for enhancing survivor outcomes, bolsters confidence in the trial's approach.

To ensure ongoing safety and integrity, risks and benefits will be continuously assessed, adjusting protocols as necessary to safeguard participant well-being. This trial aligns with best practices in cancer treatment and reflects a commitment to advancing survivor care through evidence-based lifestyle interventions.

Section 3: TRIAL OBJECTIVES, ENDPOINTS AND ESTIMANDS

Trial Objective 1: Impact of Complement Theory's Program on Quality of Life

Clinical Question: How does participation in Complement Theory's program affect Quality of Life Scores (as measured by FACT-G) in cancer survivors compared to those receiving standard care?

- Endpoint(s): Measured through change in FACT-G scores which is designed to assess various dimensions of quality of life including pain levels and sleep quality.
- Estimand(s): The mean difference in change in scores between the intervention and control groups at specified time points during and after the intervention period.

Trial Objective 2: Effect on Employee Absenteeism

Clinical Question: How does participation in the Complement Theory program influence the number of leave days taken by employed cancer survivors due to health issues?

- Endpoint(s): Number of leave days (including sick leave, short-term disability, and long-term disability) taken by participants during the trial period.
- Estimand(s): The difference in the average number of leave days between the intervention and control groups over the trial period.

Trial Objective 3: Impact on Employee Presenteeism

Clinical Question: What is the effect of Complement Theory's program on motivation to work and performance review scores among employed cancer survivors?

- Endpoint(s):

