8.2 Efficacy Assessments and Procedures

Improvement in Quality of Life (QoLS) as measured by FACT-G questionnaire (Trial Objective 1):

- Endpoint: Change in FACT-G scores measuring quality of life
- Assessment Procedures: Administer the above four questionnaires to assess participants' at baseline and specified time points during and after the intervention period.
- Data Collection: Obtain self-reported scores from participants on Quality of Life.

- Analysis: Calculate the mean difference in change in scores between the intervention and control groups at each time point to evaluate the impact of the intervention.

Reduction in Employee Absenteeism (Trial Objective 2):

- Endpoint: Number of leave days taken by employed cancer survivors due to health issues.
- Assessment Procedures: Track the number of leave days (sick leave, short-term disability, long-term disability) taken by participants in both groups throughout the trial period.
- Data Collection: Obtain leave records from participants' employers or self-reported information from participants.
- Analysis: Compare the average number of leave days between the intervention and control groups to assess the impact of the intervention on reducing absenteeism.

Improvement in Employee Presenteeism (Trial Objective 3):

- Endpoints: Motivation to work (self-reported scales/questionnaires), performance review scores (from employer records or self-reported evaluations).
- Assessment Procedures: Administer self-reported scales/questionnaires to assess participants' motivation to work and obtain performance review scores from employer records or self-reported evaluations.
- Data Collection: Collect self-reported data on motivation to work and obtain performance review scores from participants and their employers.
- Analysis: Compare the mean scores of motivation and performance reviews between the intervention and control groups to evaluate the impact of the intervention on enhancing presenteeism.

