9.1 Analysis Sets

- The analysis will include the following datasets:
 - Intent-to-Treat (ITT) set: Including all randomized survivors, regardless of their adherence with the entry criteria. This set will be used for the primary analysis of Quality of Life changes and cancer progression.
 - Per-Protocol (PP) set: Including participants who completed the trial according to the protocol without significant deviations. PP set is a subset of ITT set, excluding survivors with major protocol deviations or those who do not complete the trial. This set will be used to summarize efficacy and support sensitivity analyses.

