9.3 Analysis Supporting Secondary Objective(s)

- **Secondary Objective 1: Effect on Employee Absenteeism**

- Statistical Model and Hypothesis:
 - Model: Generalized linear models with a Poisson distribution to compare the number of leave days between groups.
 - Hypothesis: H0: No difference in the number of leave days between groups. H1: A significant reduction in leave days in the intervention group.
- Handling of Intercurrent Events:
 - Analysis will consider any change in employment status as an intercurrent event, with a modified intention-to-treat analysis excluding participants who lose their job unrelated to health status.
- Handling of Missing Data:
 - Worst-case scenario imputation for missing absenteeism data, assuming maximum observed absence for missing periods.
- Sensitivity Analysis:

- Repeating analyses with and without worst-case imputation to evaluate the impact of different missing data assumptions on the outcome.
- **Secondary Objective 2: Impact on Employee Presenteeism**
 - Statistical Model and Hypothesis:
 - Model: Mixed-effects models to analyze changes in work motivation and performance review scores over time.
 - Hypothesis: H0: No difference in changes in motivation and performance scores between groups. H1: Significant improvement in these measures in the intervention group.
 - Handling of Intercurrent Events:
 - Job changes or significant alterations in work responsibilities will be documented and explored in sensitivity analyses to understand their impact on presenteeism outcomes.
 - Handling of Missing Data:
 - LOCF for interim missing data points in motivation and performance scores, acknowledging potential limitations in this approach.
 - Sensitivity Analysis:
 - Analysis excluding participants with significant job changes during the trial to assess the effect of such changes on presenteeism outcomes.

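### Absenteeism: randomized participants who lose a job for non-health reasons are excluded, which does not match the stated estimand, and no planned analysis puts them back

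*Protocol*

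**What the plan says.** Section 3 of the Protocol (Trial Objective 2) sets the absenteeism estimand as "The difference in the average number of leave days between the intervention and control groups over the trial period". It is not limited to people who keep their job.

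Section 9.3 (Secondary Objective 1) gives the model as "Generalized linear models with a Poisson distribution to compare the number of leave days between groups", with no exposure term. On intercurrent events it says "Analysis will consider any change in employment status as an intercurrent event", and continues "with a modified intention-to-treat analysis excluding participants who lose their job unrelated to health status". That is the only handling given: nothing is said about job loss due to health, reduced hours or a new job. The one sensitivity analysis is "Repeating analyses with and without worst-case imputation to evaluate the impact of different missing data assumptions on the outcome". The Combined protocol and SAP carries the same rules in its Section 9.3, under Secondary Objective 3.

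Section 9.1 defines an ITT set and a per-protocol set, but no modified ITT set. Section 8.2 describes the data source as "Obtain leave records from participants' employers or self-reported information from participants".

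**The concern.** The rule excludes participants, not periods. Someone who works for ten months and is then laid off contributes nothing, although their leave up to that date was observed and valid.

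Whether a cancer survivor's job loss is unrelated to health is often a matter of opinion. The plan does not say who decides, on what evidence, or whether that person is blind to arm. The information may come from participants themselves, whom Section 8 says cannot feasibly be blinded (the synopsis calls the trial double-blind, so the two places conflict). Health is what the program is meant to change, so the label could depend on arm. If it does, the exclusion alone can create or hide a difference in leave days.

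The label may also matter in a second way. People whose loss is called health-related stay in. The plan does not say whether their time after job loss counts as missing. If it does, the worst-case rule would give them the maximum observed absence, so one undefined label would separate removal from the least favourable value.

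**Working it through.** **1. The plan's own figures.** Section 9.7 sizes absenteeism on two metrics, with one-sided alpha 0.05, 80% power and 1:1 allocation. If the tabled variance is read as a standard deviation, a two-sample t-test reproduces both:
- Working Hours: (40 − 30)/10 = 1.0 SD, n = 13.1, so 14 per arm, as stated.
- Vacation Days: (0.5 − 0.3)/0.15 = 1.33 SD, n = 7.73, so 8 per arm, as stated.

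The total also reproduces: 102/0.70 = 145.7, so 146. None of these figures allows for the exclusion, and no size is given for the leave-day count that Section 9.3 models. The 51 per arm are planned completers, employed or not, because Section 5.3 has no employment criterion.

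**2. Effect on power.** With the Working Hours inputs and the normal approximation, power = Φ(√(n/2) × 10/10 − 1.645). The excluded and employed shares are assumptions.

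| Excluded | n per arm, all 51 employed | Power | n per arm, 40% employed | Power |
|---|---|---|---|---|
| 0% | 51 | >0.99 | 20.4 | 0.94 |
| 10% | 45.9 | >0.99 | 18.4 | 0.92 |
| 20% | 40.8 | >0.99 | 16.3 | 0.89 |
| 30% | 35.7 | >0.99 | 14.3 | 0.85 |

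Power is little affected.

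**3. Effect on bias when there is no true effect.** All inputs here are assumed. Each person has an underlying level F, exponential with mean 1, so E[F²] = 2. Leave days are 10F. The chance of job loss is 0.15F, which averages 15% in both arms. A share p of losses is labelled unrelated to health, and those people are excluded. For simplicity, job loss does not shorten the counting period. The mean among those kept is 10 × (1 − 0.15p × 2)/(1 − 0.15p).

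| Labelled unrelated, test / control | Kept mean, test | Kept mean, control | Ratio |
|---|---|---|---|
| 50% / 50% | 10 × 0.85/0.925 = 9.19 | 9.19 | 1.00 |
| 60% / 40% | 10 × 0.82/0.91 = 9.01 | 10 × 0.88/0.94 = 9.36 | 0.96 |
| 70% / 30% | 10 × 0.79/0.895 = 8.83 | 10 × 0.91/0.955 = 9.53 | 0.93 |

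Simulating 400,000 people per arm gives the same ratios to two decimals. With everyone kept, the ratio is 1.00 throughout. If the labelling gap ran the other way, the last two ratios would invert, to 1/0.96 = 1.04 and 1/0.93 = 1.08.

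**4. Scale in days.** Suppose 3 people with 60 leave days each are excluded from an assumed 51 in one arm, and the other 48 average m days. The mean moves from (180 + 48m)/51 to m, a fall of 3(60 − m)/51:
- m = 10: 150/51 = 2.9 days
- m = 20: 120/51 = 2.4 days

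The 3 people and the 60 days are illustrative and do not come from the documents.

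**5. Comparison with the rest of the plan.** The primary endpoint (Section 9.2) uses a treatment-policy strategy for discontinuation and non-adherence. For presenteeism, also in Section 9.3, leaving out people with significant job changes is a sensitivity analysis only. Absenteeism is the one work outcome where exclusion is the stated main handling.

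**The case against.** The best defence is that the rule targets job losses unrelated to health, the kind least likely to be affected by the program. With equal labelling and equal job-loss rates the illustration shows no bias. Bias appears only when differential labelling is assumed. This stands, and it is why the harm is conditional. It does not explain why valid leave days should be discarded or why no analysis restores them.

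A reader might infer that the exclusion rests on an unblinded judgement. The documents do not support that. No adjudicator is named. Section 8 plans blinded analysts and a blinded Trial Monitoring Committee, and Section 6.6 plans blinded investigators, outcome assessors and analysts whenever possible. What can be said is that neither criteria nor blinded adjudication are stated, and that the reports may come from participants who know their arm.

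A reader might also set the rule against the ITT definition in Section 9.1, "Including all randomized survivors, regardless of their adherence with the entry criteria", and see a contradiction. There is none: the next sentence reads "This set will be used for the primary analysis of Quality of Life changes and cancer progression" and does not mention absenteeism. The gap is that the modified set is not defined there.

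Finally, counting leave only while employed is itself a choice of estimand. That is fair, and the change has to be declared.

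**Conclusion.** The point holds as a mismatch between rule and estimand. The plan excludes randomized participants on a post-randomization event, loses leave days already observed, relies on a cause-of-loss label without criteria, and offers no analysis that restores these people.

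Its size is uncertain. Spurious ratios of 0.93 to 0.96 require labelling that differs by arm, together with the assumed 15% job loss and a link between job loss and leave. In the day-count illustration, it is tempting to divide 3 × 60 = 180 days by 51 and report 3.5 days. That figure is a ceiling, reached only if the other 48 people took no leave at all, because the excluded people also leave the denominator. Since the number employed and the job-loss rate are not given, neither illustration is an estimate for this trial.

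This concerns a secondary endpoint and leaves the FACT-G analysis untouched. It is still worth correcting before unblinding, because a later choice about whom to exclude would be hard to defend.

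**What to change.** In Section 9.3 of the Protocol, and in the matching section of the Combined protocol and SAP if that remains in force:

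- Keep all randomized participants who are employed at baseline. Count leave days up to job loss, whatever its cause, with log(days employed) as an offset in the Poisson model.
- Restate the Section 3 estimand as a leave-day rate while employed.
- Report the exclusion of non-health job losses as a sensitivity analysis only, with cause classified blind to arm under written criteria.
- Add a line on the other employment changes that the section already calls intercurrent events.

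**Cost.** The estimand changes from a mean count over the trial period to a rate while employed. Counting then stops at job loss caused by ill health, which is informative and should be acknowledged when results are reported. A job-end date is also needed. It is not documented as collected: Section 8.1 lists pre-cancer work hours, sick days and disability status, and the schedule in Section 6.1 lists absenteeism questions without their content. It can be one added item in those questions. No stated sample size changes.

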 - Motivation to work: Assessed through self-reported scales or questionnaires.
 - Performance review scores: Obtained from employer records or self-reported performance evaluations.
- Estimand(s): The difference in mean scores of motivation and performance reviews between the intervention and control groups over the trial period.

Exploratory Objective(s):

Impact on rates of cancer progression, and recurrence

Clinical Question: What is the effect of Complement Theory's program on progression and recurrence of prostate, lung and colorectal cancers?

- Endpoint(s):
 - Cancer progression: Measured by changes in tumor size and changes in levels of biomarkers.
 - Recurrence: Incidence of cancer recurrence.
- Estimand(s): Directional trends evaluating the difference in proportions or rates of cancer progression and recurrence between the intervention and control groups during and post-trial follow-up.

Rationale for Excluding Breast Cancer from Exploratory Objective:

- Breast cancer, in particular, exhibits a longer average timeframe for recurrence when compared to prostate, lung and colorectal cancers. This longer latency could extend beyond the scope of our study's follow-up period, making it

challenging to accurately measure the program's impact on recurrence rates within the study's duration.

- By focusing on prostate, lung and colorectal cancers, we aim to assess the program's impact on cancers with more predictable progression patterns and well-established biomarkers, enabling a clearer evaluation of the Complement Theory's potential benefits in these specific cancer populations.

Impact on Total Healthcare Expenditure

Clinical Question: Does participation in Complement Theory's 12-month Live coactive Coaching program, focusing on Exercise and Meditation and supplemented with evidence-based information on Diet, Sleep, and other lifestyle practices, adjunct to the core treatment, lead to a reduction in total healthcare expenditure for cancer survivors?

- Endpoint(s): Total healthcare expenditure, including hospitalization costs, medication expenses, outpatient visits, and any other related healthcare services that we planned and unplanned, cancer and non-cancer, over the trial period.
- Estimand(s): The difference in mean total healthcare expenditure between the intervention and control groups over a specified period (e.g., at 12 months and 18 months from baseline).

3.1 Summary of objectives, endpoints and estimands:

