- Multivariate imputation by chained equation (MICE) will be used, i.e., filling the missing data multiple times based on the effect from other covariates by constructing a multivariate regression model. MI is superior to single imputation, as it accounts for the uncertainty of missing values in a more robust way. The number of imputations will be 10, i.e., 10 datasets with imputed data will be created. Each imputed dataset gives a point estimate of the regression coefficients as well as its standard deviation, which will be combined across the 10 datasets to obtain the final estimate and their 95% CIs.
- MICE is flexible and can accommodate variables of different types, as well as complexities such as bounded scales or survey skip patterns, making it well-suited for patient-reported outcomes like QoLS.

- **Sensitivity Analysis**

- To complement our intention-to-treat (ITT) analysis, a per-protocol analysis will be performed, including only participants who fully adhered to the intervention, to explore the effect of adherence on QoLS improvement.

- **Supplementary Analysis**

- Efficacy Analysis: survivors in the treatment and control group will be compared for the outcome variables. The comparison will be evaluated based on both SMD and P value. SMD greater than 0.2 will be considered as acceptable differences (section 3.3 indicated the definition of SMD). Descriptive statistics will be compared between treatment groups and control groups, and P values will be calculated using ANOVA tests comparing means of continuous variables, Brown-Mood test to compare the medians, and Chi-Square tests for binary and categorical variables. The differences will be considered as statistically significant within 95% confidence interval, i.e., P value less than 0.05.

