 - Analysis will consider any change in employment status as an intercurrent event, with a modified intention-to-treat analysis excluding participants who lose their job unrelated to health status.
 - Handling of Missing Data:
 - Worst-case scenario imputation for missing absenteeism data, assuming maximum observed absence for missing periods.
 - Sensitivity Analysis:
 - Repeating analyses with and without worst-case imputation to evaluate the impact of different missing data assumptions on the outcome.
- **Secondary Objective 4: Impact on Employee Presenteeism**
 - Statistical Model and Hypothesis:
 - Model: Mixed-effects models to analyze changes in work motivation and performance review scores over time.
 - Hypothesis: H0: No difference in changes in motivation and performance scores between groups. H1: Significant improvement in these measures in the intervention group.
 - Handling of Intercurrent Events:
 - Job changes or significant alterations in work responsibilities will be documented and explored in sensitivity analyses to understand their impact on presenteeism outcomes.
 - Handling of Missing Data:
 - LOCF for interim missing data points in motivation and performance scores, acknowledging potential limitations in this approach.
 - Sensitivity Analysis:

- Analysis excluding participants with significant job changes during the trial to assess the effect of such changes on presenteeism outcomes.

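### LOCF on interim presenteeism scores is unnecessary with the planned mixed model and can modestly bias interim and trial-averaged differences

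*Protocol*

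**What the plan says.** In the Protocol, Section 9.3 (presenteeism), the model is "Mixed-effects models to analyze changes in work motivation and performance review scores over time". No covariance structure is named. The missing-data rule is "LOCF for interim missing data points in motivation and performance scores, acknowledging potential limitations in this approach"; the limitations are not spelled out. Section 9.3 of the Combined protocol and SAP carries the same rule: "LOCF for interim missing data points in motivation and performance scores".

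The estimand, under Trial Objective 3 in Section 3 of the Protocol, is "The difference in mean scores of motivation and performance reviews between the intervention and control groups over the trial period". It names no single time point, so interim visits count.

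The only presenteeism sensitivity analysis is "Analysis excluding participants with significant job changes during the trial to assess the effect of such changes on presenteeism outcomes". Absenteeism, in the same section, has a missing-data check: "Repeating analyses with and without worst-case imputation to evaluate the impact of different missing data assumptions on the outcome". For the primary endpoint, Section 9.2 of the Protocol argues that "MI is superior to single imputation, as it accounts for the uncertainty of missing values in a more robust way".

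**The concern.** The imputation rule and the model do not fit together. A likelihood-based mixed model takes each participant's observed scores as they are and is valid under MAR with gaps left empty. LOCF fills the gap with an old value and passes it to the model as an observation. If scores are moving, the copied value lags behind the true one, and the model counts information that was never collected.

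Gaps are foreseeable. Section 7.1 of the Protocol allows less essential assessments to be deferred while the intervention is interrupted, for example for hospitalization or surgery, and gives priority to safety and primary-endpoint assessments. Presenteeism is a secondary endpoint, so its scores may well be among those deferred. LOCF would then carry a pre-event score across the event. Section 9.6 also schedules interim looks at secondary efficacy data at 3, 6 and 12 months, where interim differences are what is examined.

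**Working it through.** **Inputs from the documents.** Protocol Section 9.7: one-sided alpha 0.05, power 80%, 1:1 allocation; Employee Performance 0.6 against 0.7 with spread 20%; Attitude towards work 2 against 4 with spread 1.5; dropout 30%; 146 randomized. Section 6.1: motivation and performance at baseline, in odd weeks to week 47 (24 visits), and every 30 days in months 7-18.

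**Inputs assumed.** The documents give no interim gap rate. Rates of 10% to 30% per visit are used below.

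**The plan's own figures.** n per arm = 2(1.645 + 0.842)² × SD²/δ².
- Performance, with the 20% read as an SD of 0.2: 2 × 6.18 × 0.04/0.01 = 49.5, so 50. The t-test version gives 50.15, so 51 per arm and 102 in total, as stated.
- Attitude, with 1.5 read as an SD: the t-test version gives 7.73, so 8 per arm, as stated.
- 102/0.70 = 145.7, so 146.

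These figures do not involve LOCF, so removing it leaves the sample size unchanged.

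**Lag arithmetic.** Suppose each post-baseline visit is missed independently with probability p and baseline is observed. The carried value at visit j is then on average L_j = p + p² + … + p^j visits old, which tends to p/(1−p). The arm's mean falls short by slope × L_j. Under an interim-only rule the last visit has no shortfall.

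*Six visits, slopes 0.4 (test) and 0.1 (control) per visit, gaps 25% and 10%.*
- Sum of L_j over visits 1-5: 1.556 at 25%, 0.543 at 10%.
- Shortfall in the average: (0.4 × 1.556 − 0.1 × 0.543)/6 = 0.095.
- True average: 0.3 × 3.5 = 1.05. With LOCF it is 0.955, which is 9% low. A simulation of this set-up at 51 per arm (SD 1.5, correlation 0.6) gave 1.06 falling to 0.97, about 8%.
- Visit 3: 0.90 − (0.4 × 0.328 − 0.1 × 0.111) = 0.78, which is 13% low.
- Last visit: 1.80, unchanged.

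*The same total change over 24 visits, slopes 0.1 and 0.025.*
- Sum of L_j over visits 1-23: 7.556 and 2.543.
- Shortfall in the average: (0.1 × 7.556 − 0.025 × 2.543)/24 = 0.029.
- True average: 0.075 × 12.5 = 0.9375, so the average is 3% low. At late interim visits the shortfall of 0.031 is about 2% of the difference.

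*Equal slopes of 0.4 in both arms, six visits, gaps 25% and 10%.* False average difference: −0.4 × (1.556 − 0.543)/6 = −0.07, where the truth is 0.

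**Simulation of the model.** 73 per arm, effect 2, SD 1.5, visits at 0, 3, 6, 9, 12 and 18 months, effect linear to 12 months and then flat, correlation 0.6 per 6 months, gaps completely at random, unstructured covariance, 300 runs. Estimates are fractions of the final effect; the truth is 0.50, 1.00 and 1.00.

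| Setting | Analysis | 6 mo | 12 mo | 18 mo | SE 6 mo | SE 12 mo |
|---|---|---|---|---|---|---|
| 15% gaps, no dropout | observed scores | 0.500 | 1.004 | 1.004 | 0.254 | 0.255 |
| 15% gaps, no dropout | interim LOCF | 0.457 | 0.959 | 1.004 | 0.249 | 0.249 |
| 30% gaps, 30% dropout | observed scores | 0.501 | 0.999 | 0.996 | 0.273 | 0.295 |
| 30% gaps, 30% dropout | interim LOCF | 0.419 | 0.906 | 1.004 | 0.259 | 0.279 |

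With LOCF the 6-month difference is about 9% to 16% low and the 12-month difference 4% to 9% low. The standard error is about 2% to 5% below the observed-data value. A random-intercept slope model (120 runs) left the slope unchanged (1.985 against 1.982; truth 2), with standard errors 4% to 8% lower (0.190 against 0.198; 0.215 against 0.233).

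**The case against.** The plan limits LOCF to interim points, admits that the method has limitations, and collects these scores about every two weeks and then monthly. A short, isolated gap does little harm, and different endpoints may properly use different methods. Much of this stands. Effects at 3-to-6-month spacing overstate what the Section 6.1 schedule would produce, and attenuation needs both trending scores and frequent gaps. The understatement of standard errors is also soft. With unstructured covariance, the LOCF standard errors were 0.92-0.98 of the estimator's own sampling SD, much as without LOCF, and simulation error on such ratios is about 4-7%.

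A reader might infer three stronger things that the documents do not support.
- *The final difference is attenuated by about 7%.* In the six-visit set-up it falls from 1.80 to 1.68 only if a missing last visit is filled, and that is not an interim gap.
- *LOCF would exaggerate the effect if gaps were commoner in the arm that changes less.* With the rates swapped, the limiting lags are 1/9 and 1/3. Even if every gap were filled, the final difference would be 1.80 − (0.4/9 − 0.1/3) = 1.79, still slightly attenuated. With slopes in ratio 4, exaggeration needs a lag ratio above 4; here it is 3.
- *LOCF also fills scores after dropout, with a loss of about 18-27%.* Those figures arise only if the rule is extended to the 30% dropout. Section 9.3 does not extend it; it is silent on presenteeism scores after dropout.

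What the objection leaves untouched is that LOCF brings no benefit here, and that no planned analysis would show its effect.

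**Conclusion.** The point holds as a minor one. Interim LOCF is redundant with a mixed model under MAR, runs against the plan's own argument for multiple imputation, and has no companion analysis without it. Its likely effect is small. At assumed gap rates of 25% and 10%, the trial-averaged difference is about 8-9% low on six wide visits and about 3% low on the scheduled near-fortnightly visits. Standard errors are about 2-8% lower. A small false difference is possible if gap rates differ by arm. The final-visit contrast and the linear slope are not flattened. All these sizes rest on assumed gap rates, linear trends and gaps unrelated to the score; gaps tied to health events were not modelled.

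**What to change.** In Section 9.3 of both documents, delete the LOCF rule for motivation and performance scores. State that the mixed-effects model is fitted by likelihood to all observed scores, including those recorded before dropout by participants who later leave, with no imputation in the main analysis. Add the Section 9.2 multiple imputation as a sensitivity analysis, so that variables predicting missingness can be used. Naming the covariance structure in the same edit would close a related gap.

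The cost is a few lines of wording. Sample size, visits and trial conduct do not change, and the main analysis is simpler than with LOCF.
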